- Chronic use of antibiotics for prevention of AECOPD (e.g. azithromycin).
- Acute disease and/or fever at the time of first vaccination.
 - Fever is defined as temperature $\geq 37.5^{\circ}\text{C}/99.5^{\circ}\text{F}$. The preferred location for measuring temperature in this study will be the oral cavity or the axilla.
 - Subjects with a minor illness (such as mild diarrhoea, mild upper respiratory infection) without fever may be enrolled at the discretion of the investigator.
- Oxygen therapy: Use of long-term oxygen therapy (LTOT) described as resting oxygen therapy $>3\text{L}/\text{min}$ (Oxygen use $\leq 3\text{L}/\text{min}$ flow is not exclusionary).
- Planned lung transplantation.
- Lung resection: Subjects with planned lung volume reduction surgery during the study or within the 12 months prior to first vaccination.
- Diagnosis of α -1 antitrypsin deficiency as the underlying cause of COPD.

- Diagnosed with a respiratory disorder other than COPD at time of enrolment (such as sarcoidosis, active tuberculosis, clinically significant bronchiectasis, clinically significant lung fibrosis, clinically significant pulmonary embolism, clinically significant pneumothorax, current diagnosis of asthma in the opinion of the investigator), or chest X-ray/ CT scan revealing evidence of clinically significant abnormalities not believed to be due to the presence of COPD. Subjects with allergic rhinitis do not need to be excluded and may be enrolled at the discretion of the investigator.
- History of immune-mediated disease other than COPD.

Please refer to [Table 19](#) for a non-exhaustive List of potential immune-mediated diseases. If the subject has any condition on this list, they must be excluded unless the aetiology is clearly documented to be non-immune mediated.

The investigator will exercise his/her medical and scientific judgement in deciding whether other diseases have an autoimmune origin and thus meet the exclusion criteria.

- Previous vaccination with any vaccine containing NTHi and/ or Mcat antigens.
- History of any reaction or hypersensitivity likely to be exacerbated by any component of the vaccines and/ or the bronchodilator used for spirometry assessment during the study.
- Contraindication for spirometry testing (such as recent eye surgery, recent thoracic or abdominal surgery procedures, unstable cardiovascular status, recent myocardial infarction or pulmonary embolism).

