* In case an emergency mass vaccination for an unforeseen public health threat (e.g.: a pandemic) is organised by the public health authorities, outside the routine immunisation program, the time period described above can be reduced if necessary for that vaccine provided it is licensed and used according to its Prescribing Information and according to the local governmental recommendations and provided a written approval of the Sponsor is obtained.

- Immunoglobulins or any blood products administered at any time during the study period.
- Immunosuppressants or other immune-modifying drugs administered chronically (i.e. more than 14 days) at any time during the study period (e.g. methotrexate). Use of corticosteroids is allowed as per local treatment recommendations.

7.6.3. Concomitant medications/ products/ intervention that may lead to the elimination of a subject from the per-protocol analysis for efficacy

In addition to the concomitant medications/ products/ vaccines described in the Section 7.6.2, the use of the following medications/ products/ intervention will not require withdrawal of the subject from the study but may determine a subject's evaluability in the per-protocol analysis for efficacy.

- Underwent lung transplantation/ lung resection surgery at any time during the entire study period.
- Chronic use of antibiotics at any time during the entire study period.

7.7. Intercurrent medical conditions that may lead to elimination of a subject from per-protocol analyses

At each study visit subsequent to the first vaccination, it must be verified if the subject has experienced or is experiencing any intercurrent medical condition. If it is the case, the condition(s) must be recorded in the eCRF.

Subjects may be eliminated from the per-protocol cohort for immunogenicity and efficacy if, during the study, they incur a condition that has the capability of altering their immune response or are confirmed to have an alteration of their initial immune status.

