11.5.3. Modified total vaccinated cohort

The modified total vaccinated cohort (mTVC) will include all subjects with 2 documented study vaccine administrations with respect to the vaccine actually administered.

The primary efficacy analysis will be performed on the mTVC.

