11.5.4. Per-protocol set for analysis of immunogenicity

The per-protocol set (PPS) for immunogenicity will include all subjects in the TVC:

- Who met all eligibility criteria.
- For whom the administration of the vaccines was according to protocol.
- Who complied with the vaccination schedule, as specified in [Table 8](#).
- Who received the study vaccines according to protocol procedures.
- Who did not receive a concomitant medication/ product leading to elimination from the PPS (per-protocol) analysis for immunogenicity (see Section [7.6.2](#)) up to the 1 month post--Dose 2 visit (Day 91).
- Who did not present an intercurrent medical condition leading to elimination from the PPS analysis for immunogenicity (see Section [7.7](#)), up to the 1 month post--Dose 2 visit (Day 91).
- Who complied with the blood sample timings as specified in [Table 8](#), at the 1 month post-Dose 2 visit (Day 91).
- For whom post-vaccination immunogenicity results are available for at least 1 assay.

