11.5.5. Per-protocol set for analysis of efficacy

The PPS for analysis of efficacy will include all subjects in the TVC:

- Who met all eligibility criteria.
- For whom the administration of the vaccines was according to protocol.
- Who complied with the vaccination schedule, as specified in [Table 8](#).
- Who received the study vaccine according to protocol procedures.
- Not having received a medication/ product/ vaccine that may lead to elimination from the PPS (per-protocol) analysis for efficacy (see Section [7.6.3](#)).

In addition, for the Bacteriological efficacy endpoints:

- For whom the sputum sample results are available.

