11.8. Analysis of efficacy

The primary analysis will be performed on the mTVC and repeated on the TVC **and the FAS**. The primary analysis will also be repeated on the efficacy ATP (per-protocol) cohort if the percentage of vaccinated subjects excluded from the ATP cohort for efficacy is more than 5%.

Efficacy – Clinical Endpoint

The following incidence rates of AECOPD (any type) occurring from enrolment up to 1 month post-Dose 2 will be computed together with **95% CI**, and incidence rates together with VE in the prevention of AECOPD (any type) will be computed over a period starting 1 month post-Dose 2 and lasting for 1 year, with **95% CI**:

- All-cause moderate and severe AECOPD (primary endpoint).
- All-cause, all-severity AECOPD.
- All-cause AECOPD, by severity.

For the primary endpoint, the 87% CI will also be reported in order to evaluate the null hypothesis at 13% alpha level (2-side). This objective will be considered a success if the lower limit of the 87% CI will be above 0%. (Amended 27 March 2019)

The CIs of the incidence rate will be computed using a model which accounts for repeated events. The primary outcome will be analysed using the Negative Binomial regression model with number of AECOPD as dependent variable; treatment (vaccine or placebo), age group (40–59 years or 60–80 years), GOLD grade (2, 3 or 4), history of exacerbations (<2 or ≥ 2) and country as independent variables, with logarithm as link function, and the logarithm of time for follow-up (in years) as an offset variable. If the model does not converge, the Poisson distribution will be used instead of the Negative Binomial one.

VE for AECOPD events is defined as:

$$VE(\text{AECOPD}) = 1 - R_{\text{vacc}} / R_{\text{con}}$$

with:

- R_{vacc} = average yearly incidence rate of AECOPD events per subject in the group 10-10-3-AS.
- R_{con} = average yearly incidence rate of AECOPD events per subject in the Control group.

Incidence rates of AECOPD (any type) and VE, together with 95% CI, will be computed for the following time periods:

- At Month 3, 6, 9, 12, 15 from Day 1 (cumulative)
- By 6 Months follow up period (from 1 month post-Dose 2)
- By 3 Months follow up period (from 1 month post-Dose 2)

The model used will be the same as for the primary analysis.

A sensitivity analysis **using** a permutation test will be performed for the primary efficacy endpoint.

Efficacy – Bacteriological Endpoint (PCR)

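### Removing whole subjects from the efficacy per-protocol set for chronic antibiotics started during follow-up would pull the per-protocol VE towards zero if the vaccine works and prescribing follows AECOPD

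*Protocol*

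**What the plan says.** - **Elimination rule.** Section 7.6.3 names "Chronic use of antibiotics at any time during the entire study period" as a use that "may determine a subject's evaluability in the per-protocol analysis for efficacy".
- **How the set applies it.** Section 11.5.5 includes in the efficacy per-protocol set subjects described as "Not having received a medication/ product/ vaccine that may lead to elimination from the PPS (per-protocol) analysis for efficacy". It states no time limit and no censoring at the start of the medication.
- **Entry.** Section 5.3 excludes "Chronic use of antibiotics for prevention of AECOPD (e.g. azithromycin", and also any systemic antibiotic in the 30 days before first vaccination.
- **Meaning of chronic.** Section 7.6.2 gives a duration (more than 14 days) for immunosuppressants. No duration is given for antibiotics.
- **Where the set is used.** "The primary efficacy analysis will be performed on the mTVC" (11.5.3), with repeats on the TVC and FAS (11.8). Section 11.8 adds: "The primary analysis will also be repeated on the efficacy ATP (per-protocol) cohort if the percentage of vaccinated subjects excluded" exceeds 5%.
- **Model.** Section 11.8 uses negative binomial regression with log follow-up time as offset. Section 11.6 assumes missingness is MCAR or MAR.

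**The concern.** Membership of the efficacy per-protocol set depends on a treatment given after randomisation whose purpose, as 5.3 words it, is to prevent the primary endpoint. The natural recipients are subjects who have already had several AECOPD. The rule drops such a subject completely: one with four events who starts prophylaxis late in follow-up contributes none of them. If the vaccine lowers the AECOPD rate, fewer vaccinees reach that state, so deletion thins the upper tail of the placebo arm more than that of the vaccine arm.

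The absence of a definition of *chronic* for antibiotics adds to this. Moderate AECOPD is defined by systemic corticosteroids and/or antibiotics (Table 1), and 11.6 describes treatment courses of up to 2 to 4 weeks. Read loosely, the rule could let treatment of an endpoint event remove the subject who had it.

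At stake is how a planned repeat of the primary analysis is read. A per-protocol VE below the mTVC estimate through selection alone could be taken as fragility, or as the vaccine working less well in compliant subjects.

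**Working it through.** **Inputs from the protocol (11.4).** Placebo rate 0.8 per year; vaccine rate 0.8 × 0.72 = 0.576 (VE 28%); over-dispersion 1.8; two-sided alpha 13%; power 80%; drop-out 15%.

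**Reproducing the plan's figure.** Take over-dispersion as 1 + k × 0.8, so k = 0.8/0.8 = 1. Then n = (1.514 + 0.842)² × (1/0.8 + 1/0.576 + 2k) / (ln 0.72)² = 5.549 × 4.986 / 0.1079 = 256.4. This rounds up to 257 per group, as in Table 23. The same negative binomial model is used below.

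**Assumption not in the documents.** Chronic antibiotics start with probability p after each moderate or severe AECOPD from the c-th onwards. One full year of follow-up; no effect of the antibiotic on later events.

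**Formula.** With k = 1 the yearly count is geometric: P(N = n) = q·aⁿ, with q = 1/(1+m), a = m/(1+m) and m the arm's mean. A subject with n ≥ c events stays in the set with probability (1−p)^(n−c+1). For c = 2 and s = 1−p:

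- share kept: K = q[1 + a + a²s/(1−as)]
- mean count among those kept: q·a / [(1−as)²·K]

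**Worked case, c = 2, p = 0.3.**

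- Placebo (a = 0.4444): K = 0.914, so 8.6% are deleted; mean 0.569.
- Vaccine (a = 0.3655): K = 0.946, so 5.4% are deleted; mean 0.443.
- Per-protocol VE = 1 − 0.443/0.569 ≈ 22%.

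**Range (true VE 28%; deletions are placebo / vaccine / pooled).**

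| Start from | p | Deleted | Per-protocol VE |
|---|---|---|---|
| 2nd AECOPD | 3% | 1.0 / 0.6 / 0.8% | 27.4% |
| 2nd | 10% | 3.3 / 2.0 / 2.6% | 25.9% |
| 2nd | 25% | 7.4 / 4.6 / 6.0% | 23.1% |
| 2nd | 30% | 8.6 / 5.4 / 7.0% | 22.2% |
| 2nd | 50% | 12.7 / 8.2 / 10.4% | 19.1% |
| 3rd | 3% | 0.5 / 0.2 / 0.3% | 27.4% |
| 3rd | 30% | 3.8 / 2.0 / 2.9% | 23.2% |
| 3rd | 50% | 5.6 / 3.0 / 4.3% | 21.0% |

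If antibiotics also cut later AECOPD by 30%, simulation gives 22.8% (2nd event, p = 25%) and 21.1% (3rd event, p = 50%), close to the table.

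**Null case.** If both arms have the same mean, the formula deletes the same share and leaves the same mean in each, so VE stays at 0.

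**Censoring instead of deleting.** Event-by-event simulation, with the negative binomial model and log-time offset fitted to data cut at antibiotic start, returns about 28% for p = 3% to 50% from the 2nd or 3rd event. The start depends only on AECOPD already counted, which is what MAR allows.

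**Scale against sampling error.** With 0.85 × 300 = 255 completers per arm, the standard error of VE is about 0.72 × √(4.986/255) = 0.10. A shift of 1 to 9 points is about 0.1 to 0.9 of a standard error.

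**The case against.** **No decision rests on this set.** True. Success is judged on the 87% CI of the primary analysis in the mTVC, and the TVC and FAS repeats do not use the antibiotic rule. A reader might infer that the primary result is compromised; the documents do not support that.

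**The repeat may never be run.** It needs more than 5% excluded. In the table this rule alone passes that mark only from the 2nd event at p = 25% and above. Other exclusions can add to it, but antibiotic users are then only part of the deletions.

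**The size rests on an assumed start rate.** True. At 3% per event the loss is under 1 point. A certain or large bias cannot be claimed.

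**Section 7.6.3 says only that such use may affect evaluability, and it covers chronic antibiotics for any reason.** This stands as a limit on certainty. Section 11.5.5 nevertheless works as a subject-level criterion and offers no alternative to removal.

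**The Day 91 limit in the immunogenicity set.** It is tempting to call the absence of such a limit in the efficacy set an internal inconsistency. It is not: the between-group immunogenicity comparison is at 1 month post-Dose 2 (11.9.2), while the efficacy endpoint covers the following year.

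**Other listed treatments.** A reader might extend the point to blood products, immunosuppressants and lung surgery. None was modelled, and corticosteroids, the obvious AECOPD-driven drug, are expressly allowed in 7.6.2.

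**Excluding users of a confounding treatment is conventional, and censoring targets a different quantity.** Partly fair. The recovery to 28% was also obtained in data generated from the model that was fitted. But deletion discards outcome data from before the treatment began, which a per-protocol aim does not require.

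**Conclusion.** The point holds for chronic antibiotics in the efficacy per-protocol set. Whole-subject removal for use at any time makes membership depend on the outcome. With a true VE of 28% and AECOPD-driven prescribing at 3% to 50% per event, the per-protocol VE would be about 27% down to 19%. This rests on three conditions: the vaccine works, antibiotic starts follow AECOPD, and the permissive wording of 7.6.3 is applied as removal. The documents make the second plausible but do not quantify it.

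The bias is towards zero, vanishes when VE is 0, and cannot create a false success. It touches one conditional, supportive analysis. It is worth correcting because the correction is cheap, not because the trial's main conclusion is at risk.

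**What to change.** In 7.6.3 and 11.5.5:

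1. For chronic antibiotics first started after the efficacy window opens (1 month post-Dose 2), keep the subject in the efficacy per-protocol set and censor both follow-up time and AECOPD count at the start date. The existing log-time offset handles the shorter follow-up.
2. Keep whole-subject elimination for chronic antibiotics started before the window opens.
3. State, for the analysis only, what counts as *chronic* for antibiotics, so that a treatment course for an AECOPD does not trigger the rule.

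The mTVC, TVC and FAS analyses, sample size, visits and treatment are unchanged. The cost is a wording change and one derived date. Section 7.6.1 already requires concomitant medication to be recorded from Day 1 to Day 451 but does not mention start dates, so that eCRF field should be confirmed. The small downside is that the censored analysis relies on MAR, which 11.6 already assumes.

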8. HEALTH ECONOMICS

Not applicable.

9. SAFETY

The investigator or site staff is/are responsible for the detection, documentation and reporting of events meeting the criteria and definition of an AE or SAE as provided in this protocol.

Each subject will be instructed to contact the investigator immediately should they/the subject manifest any signs or symptoms they perceive as serious.

9.1. Safety definitions

9.1.1. Definition of an adverse event

An AE is any untoward medical occurrence in a clinical investigation subject, temporally associated with the use of a medicinal product, whether or not considered related to the medicinal product.

An AE can therefore be any unfavourable and unintended sign (including an abnormal laboratory finding), symptom, or disease (new or exacerbated) temporally associated with the use of a medicinal product. For marketed medicinal products, this also includes failure to produce expected benefits (i.e. lack of efficacy), abuse or misuse.

Examples of an AE include:

- Significant or unexpected worsening of the condition under study.
- Exacerbation of a chronic or intermittent pre-existing condition, apart from the condition under study, including either an increase in frequency and/or intensity of the condition.
- New conditions detected or diagnosed after investigational vaccine administration even though they may have been present prior to the start of the study.
- Signs, symptoms, or the clinical sequelae of a suspected interaction.
- Signs, symptoms temporally associated with vaccine administration.
- Pre- or post-treatment events that occur as a result of protocol-mandated procedures (i.e. invasive procedures, modification of subject's previous therapeutic regimen).

AEs to be recorded as endpoints (solicited AEs) are described in Section 9.1.3. All other AEs will be recorded as UNSOLICITED AEs.

Examples of an AE DO NOT include:

- Medical or surgical procedures (e.g. endoscopy, appendectomy); the condition that leads to the procedure is an AE/ SAE.
- Situations where an untoward medical occurrence did not occur (e.g. social and/or convenience admission to a hospital, admission for routine examination).
- Anticipated day-to-day fluctuations of pre-existing disease(s) or condition(s) present or detected at the start of the study that do not worsen.
- The disease being studied, or expected progression, signs, or symptoms of the disease being studied, unless more severe than expected for the subject's condition.
- Pre-existing conditions or signs and/or symptoms present in a subject prior to the first study vaccination. These events will be recorded in the medical history section of the eCRF.

9.1.2. Definition of a serious adverse event

A SAE is any untoward medical occurrence that:

- a. Results in death,
- b. Is life-threatening,

Note: The term 'life-threatening' in the definition of 'serious' refers to an event in which the subject was at risk of death at the time of the event. It does not refer to an event, which hypothetically might have caused death, had it been more severe.

- c. Requires hospitalisation or prolongation of existing hospitalisation,

Note: In general, hospitalisation signifies that the subject has been admitted at the hospital or emergency ward for observation and/or treatment that would not have been appropriate in the physician's office or in an out-patient setting. Complications that occur during hospitalisation are also considered AEs. If a complication prolongs hospitalisation or fulfils any other serious criteria, the event will also be considered serious. When in doubt as to whether 'hospitalisation' occurred or was necessary, the AE should be considered serious.

Hospitalisation for elective treatment of a pre-existing condition (known or diagnosed prior to informed consent signature) that did not worsen from baseline is NOT considered an AE.

- d. Results in disability/incapacity, OR

Note: The term disability means a substantial disruption of a person's ability to conduct normal life functions. This definition is not intended to include experiences of relatively minor medical significance such as uncomplicated headache, nausea, vomiting, diarrhoea, influenza like illness, and accidental trauma (e.g. sprained ankle) which may interfere or prevent everyday life functions but do not constitute a substantial disruption.

- e. Is a congenital anomaly/birth defect in the offspring of a study subject.

Medical or scientific judgement should be exercised in deciding whether reporting is appropriate in other situations, such as important medical events that may not be immediately life-threatening or result in death or hospitalisation but may jeopardise the subject or may require medical or surgical intervention to prevent one of the other outcomes listed in the above definition. These should also be considered serious.

Examples of such events are invasive or malignant cancers, intensive treatment in an emergency room or at home for allergic bronchospasm, blood dyscrasias or convulsions that do not result in hospitalisation.

9.1.3. **Solicited adverse events**

Solicited local and general AEs occurring during a 7-day follow-up period after each vaccination (i.e. the day of vaccination and the 6 subsequent days), will be reported via eDiary for vaccine reactogenicity. **(Amended 27 March 2019)** Unsolicited AEs occurring during a 30-day follow-up period after each vaccination (i.e. the day of vaccination and the 29 subsequent days), will be reported at Phone Contacts and Clinical Visits, and recorded via the appropriate section of the eCRF.

9.1.3.1. **Solicited local (injection-site) adverse events**

The following local (injection-site) AEs will be solicited:

Table 17 Solicited local adverse events

Pain at injection site
Redness at injection site
Swelling at injection site

9.1.3.2. **Solicited general adverse events**

The following general AEs will be solicited:

Table 18 Solicited general adverse events

Fatigue
Fever
Gastrointestinal symptoms [†]
Headache
Myalgia
Chills

[†]Gastrointestinal symptoms include nausea, vomiting, diarrhoea and/or abdominal pain.

Note: Subjects will be instructed to measure and record the oral or axillary body temperature in the evening. Should additional temperature measurements be performed at other times of day, subjects will be instructed to record the highest temperature in the eDiary.

9.1.4. **Clinical laboratory parameters and other abnormal assessments qualifying as adverse events or serious adverse events**

In absence of diagnosis, abnormal laboratory findings (e.g. clinical chemistry, haematology, urinalysis) or other abnormal assessments that are judged by the investigator to be clinically significant will be recorded as AE or SAE if they meet the definition of an AE or SAE (refer to Sections 9.1.1 and 9.1.2). Clinically significant abnormal laboratory findings or other abnormal assessments that are present at baseline and significantly worsen following the start of the study will also be reported as AEs or SAEs.

The investigator will exercise his or her medical and scientific judgement in deciding whether an abnormal laboratory finding or other abnormal assessment is clinically significant.

